### 3.3.2 Exclusion criteria

- 1) Inflammatory breast cancer.
- 2) The tumor is extensive and it's difficult to achieve negative margins or an ideal breast - conserving appearance.
- 3) Diffusely distributed malignant - characteristic calcifications.
- 4) The margin is positive after local extensive tumor resection, and a negative margin in pathological examination still can't be ensured after re - resection.
- 5) The patient refuses.

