### 3.2 Technical route

### 3.3 Study population

#### 3.3.1 Inclusion criteria

- 1) The patient himself has very high requirements for beauty, and requires no scar on the chest;
- 2) No chest surgery and radiotherapy.
- 3) No contraindications to surgery and anesthesia.
- 4) Clinical I, stage of early breast cancer and the breast has an appropriate volume, can maintain a good breast shape after surgery.
- 5) Patients in the clinical period who meet the standard of breast conservation

surgery after preoperative treatment.

6) Age: 18 and 65 years old.

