### 3.3.3 Exit criteria

- 1) Those who cannot complete the single-port robot breast conserving surgery and need to be converted into traditional breast conserving surgery or endoscopic breast preservation surgery.
- 2) The patient voluntarily requests to withdraw from the investigator.
- 3) The patient is associated with other non-tumor conditions so that they cannot continue to accept the study program;
- 4) After inclusion in the study, the investigator cannot be completed due to other reasons.

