### 3.8 Endpoint evaluation index

To verify the safety and efficacy of the single-port robot (SPr) in breast conserving surgery, the primary endpoint of this study was the success rate of breast conserving surgery. Successful breast-conserving surgery was determined by a negative tumor margin at least 2-3mm from normal tissue, and secondary endpoints included postoperative pain score and cosmetic score.

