#### 4.2 Statistical analysis of the population

This study, conducted only in the Army Characteristic Medical Center, is a single-center, prospective clinical cohort study designed to evaluate the safety and efficacy of single-port robots in breast cancer surgery by comparison with the traditional breast-conserving surgery group. During the trial, the clinical data will be

reviewed centrally to ensure uniform quality.

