#### 4.3 Preliminary analysis

Two-person data entry was performed using Excel 2010 and SPSS 25.0 data analysis. Baseline numerical data will be described as mean, standard deviation or median and interquartile range, and baseline categorical data will be shown as percentage. Normality and homogeneity of variance of continuous variables were tested by Kolmogorov-Smirnov test and ANA variance, respectively. Independent sample t-test for continuous variables meeting normal distribution and homogeneity of variance, Mann Whitney U test for continuous variables not meeting normal distribution, and Fishers exact test and Pearson chi square test for categorical variables and count data. Primary endpoint analysis: The success rate of breast conservation surgery under single hole robot will be compared by Chi-square test (Chi-square test) with exact test if necessary. Use multiple interpolation methods to deal with missing data. Postoperative cosmetic score and postoperative pain score were calculated and analyzed according to the standard scale.

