#### 4.4 Effectiveness analysis

The primary endpoint of this study is the success rate of breast-conserving surgery in patients with breast cancer. The success of breast-conserving surgery was determined by a negative tumor margin at least 2-3mm from normal tissue. Secondary endpoints included surgical specimen quality, functional outcome, and quality of life (postoperative pain score, postoperative cosmetic score).

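### Exclusion criterion 4, as written, removes patients who fail the primary endpoint, so success rates are biased upward and a group difference can be hidden

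*SAP*

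**What the plan says.** **Endpoint.** SAP 3.8 defines the primary endpoint: "Successful breast-conserving surgery was determined by a negative tumor margin at least 2-3mm from normal tissue". Section 4.4 repeats it: "The success of breast-conserving surgery was determined by a negative tumor margin at least 2-3mm from normal tissue". Neither says whether the margin at first excision or after re-resection is judged.

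**Exclusions (3.3.2).** Item 4 reads "The margin is positive after local extensive tumor resection, and a negative margin in pathological examination", and continues that the negative margin still cannot be assured after a further resection. Item 2 separately excludes extensive tumours where it is "difficult to achieve negative margins or an ideal breast - conserving appearance".

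**Inclusion (3.3.1).** Item 2 requires "No chest surgery and radiotherapy".

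**Exit (3.3.3).** Item 1 lists "Those who cannot complete the single-port robot breast conserving surgery and need to be converted into traditional breast conserving surgery", or to the endoscopic operation.

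**Analysis.** Section 4.2, headed as the analysis population, describes only the design: the study is "designed to evaluate the safety and efficacy of single-port robots in breast cancer surgery by comparison with the traditional breast-conserving surgery group". It defines no analysis set. Under 4.3 the success rate "will be compared by Chi-square test (Chi-square test) with exact test if necessary", with no statement of who is in the denominator.

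**The concern.** A margin that stays positive is both a reason for exclusion and a failure of the only primary endpoint. If item 4 is applied after pathology, patients leave because of their outcome. Each group's success rate then rises, and it rises more in the group with more uncleared margins. This can hide the very disadvantage of a new technique that the study should be able to show.

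The robot group has only 20 patients, so one or two removals change the result visibly. The study is also unblinded and non-randomised, so discretion to drop a patient once the result is known should be closed in advance. The missing-data method in 4.3 does not help, because the outcome of these patients is observed, not missing. If their data are not kept, no later analysis can repair the loss.

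**Working it through.** **Which operation does item 4 mean?** It depends on pathology after a resection and a re-resection. For a patient who meets inclusion item 2 (no earlier chest surgery), the natural source of that pathology is the study operation. Exclusion item 2 already covers tumours where clear margins are expected to be difficult, so a purely preoperative reading leaves item 4 little to add.

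**Inputs.** Group sizes are 20 robot patients, with 80 controls in the Scenario summary or 60 in 4.1. The document gives no margin-failure rate and derives no sample size, so it has no figure of its own to reproduce. All rates below are assumptions:
- F: share whose margin is never cleared (2%, 5%, 10%).
- C: share with a final margin that is negative but too close (0%, 5%, 10%).
- P: share failing at first excision (10%, 20%, 30%), which includes F.

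**Expected removals, n × F.**

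| F | 20 robot | 60 controls | 80 controls |
|---|---|---|---|
| 2% | 0.4 | 1.2 | 1.6 |
| 5% | 1 | 3 | 4 |
| 10% | 2 | 6 | 8 |

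**Bias if the final margin counts.** True success = 1 − F − C. Reported success = (1 − F − C)/(1 − F).

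| F | C = 0 | C = 5% | C = 10% | Bias (points) |
|---|---|---|---|---|
| 2% | 98.0 → 100 | 93.0 → 94.9 | 88.0 → 89.8 | 1.8-2.0 |
| 5% | 95.0 → 100 | 90.0 → 94.7 | 85.0 → 89.5 | 4.5-5.0 |
| 10% | 90.0 → 100 | 85.0 → 94.4 | 80.0 → 88.9 | 8.9-10.0 |

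Example: (1 − 0.05 − 0.05)/(1 − 0.05) = 0.90/0.95 = 94.7%, against a true 90.0%.

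**Bias if the first margin counts.** True success = 1 − P. Reported success = (1 − P)/(1 − F).

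| F | P = 10% | P = 20% | P = 30% | Bias (points) |
|---|---|---|---|---|
| 2% | 90.0 → 91.8 | 80.0 → 81.6 | 70.0 → 71.4 | 1.4-1.8 |
| 5% | 90.0 → 94.7 | 80.0 → 84.2 | 70.0 → 73.7 | 3.7-4.7 |
| 10% | 90.0 → 100 | 80.0 → 88.9 | 70.0 → 77.8 | 7.8-10.0 |

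**Effect on the comparison (final margin).** With C = 5% and F = 10% robot against 5% control, true success is 85% against 90% and reported success is 94.4% against 94.7%. A 5.0-point difference becomes 0.3 points. Example tables, with Fisher's exact test, two-sided:

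| All started operations | p | After item 4 | p |
|---|---|---|---|
| 18/20 vs 76/80 | 0.60 | 18/18 vs 76/76 | 1 |
| 16/20 vs 76/80 | 0.049 | 16/16 vs 76/76 | 1 |
| 16/20 vs 57/60 | 0.062 | 16/16 vs 57/57 | 1 |
| 13/20 vs 72/80 (some close margins) | 0.011 | 13/14 vs 72/76 | 0.58 |

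The first row lies within the assumed 2-10% range for F. The others assume 20% or 30% uncleared margins in the robot group and are more extreme.

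**Precision.** The exact 95% interval for 18/20 is 68.3-98.8%. For 18/18 it is 81.5-100%. Removing two failures lifts the lower limit by 81.5 − 68.3 = 13.2 points.

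**The case against.** The best defence is that item 4 is an entry screen. Sections 3.1 and 3.4.1 place enrolment and preoperative evaluation before surgery. Removal after inclusion has its own list in 3.3.3, and a persistently positive margin is not on it. Item 4 may be a general contraindication to breast conservation, or may describe a patient referred after an earlier excision, since the ban on chest surgery is not defined precisely. Items 2 and 4 also concern different facts: an extensive tumour and a pathology result. This reading is possible, but the document states it nowhere, and no section says that a study patient with an uncleared margin is kept as a failure.

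On size, the objection is partly right. All rates are assumed. At 2-5%, only 0.4-1 robot patient is expected to be removed. The example that crosses 0.05 needs 20% uncleared margins in the robot group, and with 60 controls it does not cross. At 18/20 against 76/80 no significant result is lost. If F is equal in both groups, the rates are inflated but little or no difference is hidden. A collapse to 100% in both groups needs the final margin to count and no close margins. None of this removes the upward bias.

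A further point stands. Section 3.3.3 does not say that data from converted patients leave the analysis, and the Scenario summary makes conversion a safety measure, which requires counting them. Exit criterion 1 is therefore in tension with a rule to analyse every started operation; it is not a proven contradiction.

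**Conclusion.** The concern holds: item 4 is wrong as written and must be fixed. Read literally, it selects patients on the primary outcome, and nothing in 3.8, 4.2, 4.3 or 4.4 puts them back. If it is applied after surgery, success is overstated whenever any margin stays uncleared and any success remains. The overstatement is close to the uncleared-margin rate itself, or somewhat less when other failures are common. Hiding a group difference requires that rate to differ between the groups.

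The direction follows from the wording. The size rests on assumed rates. Confidence is medium, because item 4 may have been intended as a preoperative contraindication.

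**What to change.** - **3.3.2:** delete item 4 as an exclusion, or limit it to what is known before the study operation.
- **3.8, 4.2 and 4.4:** state that every eligible patient in whom the study operation is started stays in the primary analysis, in the group of the operation started, and that a margin not made negative counts as failure.
- **3.3.3:** reconcile exit criterion 1 with this rule, so that converted robot patients stay in the analysis. State in advance how a conversion with a negative margin is counted.
- **3.8 and 4.4:** state whether success is judged at first excision or after re-resection, and report the other as supportive. Replace the 2-3 mm range with one cut-off, chosen by the sponsor before any pathology is analysed, so that the failure rule can be applied.

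The cost is wording in five sections. No extra patients or procedures are needed. Reported success rates may be slightly less favourable.

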### 3.3.3 Exit criteria

- 1) Those who cannot complete the single-port robot breast conserving surgery and need to be converted into traditional breast conserving surgery or endoscopic breast preservation surgery.
- 2) The patient voluntarily requests to withdraw from the investigator.
- 3) The patient is associated with other non-tumor conditions so that they cannot continue to accept the study program;
- 4) After inclusion in the study, the investigator cannot be completed due to other reasons.

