## Scenario summary

research topic	Application of Single-Port Robot-Assisted Breast-Conserving Surgery via Axillary Approach for Breast Cancer.
Main purpose of the study	
1. To evaluate the efficacy of single-port robots in breast cancer breast conserving surgery. Including differences in operative time and intraoperative number of lymph nodes detected.
 
2. To evaluate surgical safety: the incidence of surgical transfer and the incidence of postoperative complications.

Secondary purpose of the study	Pain and cosmetic scores of patients after breast conserving surgery under a single port robotic approach.
research design	
 Randomized controlled trial
 
 non-randomized controlled study
 
 Single-arm study
 
 Other
 
 Single-center study    multicenter study
 
Whether blind:  yes  no

subject investigated	Patients undergoing breast-conserving surgery for breast cancer.
intervention study	Single-port Robot-assisted breast-conserving surgery for breast cancer.
endpoint criteria	Success rate of breast conservation surgery under single-port robotic approach
sample capacity	Total number of cases: 100; 20 in the test group; 80 in the control group

statistical analysis	Double data entry was carried out using Excel 2010, and data analysis was performed with SPSS 25.0. The normality of continuous variables and homogeneity of variance were examined by Kolmogorov-Smirnov test and analysis of variance test respectively. For continuous variables that conformed to normal distribution and had homogeneity of variance, the independent-samples t-test was adopted. For continuous variables that did not conform to normal distribution, the Mann Whitney U test was used. For categorical variables and count data, Fisher's exact test and Pearson chi square test were employed.
Study cycle	November 2024-December 2025

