## 3. Research Design

### 3.1 Overall Study Design

-Enrollment: Subjects who meet the inclusion criteria enter the study process, including SPr-breast conserving surgery or Traditional-breast conserving surgery. The choice of the two surgical methods is based on the patients economic situation and the availability of equipment.

-Preoperative hospitalization: Collect patient disease information (including mammography, breast B ultrasound, breast enhanced MRI, etc.).

-The day of operation: Record the operation time, intraoperative bleeding volume, intraoperative complications, intraoperative adverse events, etc.

-Postoperative hospitalization: Record postoperative complications (postoperative bleeding, flap or nipple areola complex necrosis, subcutaneous emphysema, infection, capsular spasm, postoperative shoulder pain and discomfort, etc.), postoperative pain score, and postoperative pathological biopsy.

-Postoperative hospital stay: Calculated based on the number of days from surgery to discharge.

[figure not shown]
-28 days after surgery: To understand the complication rate and mortality rate within 28 days after surgery.

-90 days after surgery: To understand the complication rate and mortality rate within 90 days after surgery.

-Disease-free survival at 3 years after surgery (recurrence was defined as surgical area and distant metastasis by the time from surgery to last follow-up or date of recurrence and metastasis).

-3 year overall survival (from time from surgery to last follow-up or death).

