**(3) Standards for suspending or modifying the planned procedure:**

Conversion of SPr-breast conserving surgery to endoscopic or traditional breast conserving surgery is interruption due to technical difficulties or complications during intraoperative anatomical procedures that need to enable an open field conversion for further processing. Surgeons decide whether to switch to endoscopy or open for breast surgery amid concerns about patient safety, technical difficulties, inability to adequately complete robotic surgery or require treatment for related diseases.

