#### 3.8.1 Primary endpoint indicators

Success rate of breast conserving surgery under single port robotic transaxillary approach.

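### Exit criterion 1 removes converted patients from the robot group only, and no analysis set keeps them, so 28- and 90-day complications would be expected to look better for the robot than they were

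*SAP*

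**What the plan says.** - **SAP 3.3.3, item 1**, names as patients who exit: "Those who cannot complete the single-port robot breast conserving surgery and need to be converted into traditional breast conserving surgery"; the item goes on to include endoscopic surgery.
- **SAP 3.5 (3)** describes conversion as "interruption due to technical difficulties or complications during intraoperative anatomical procedures". It also lets the surgeon convert for patient safety, inability to complete the robotic operation, or treatment of related disease.
- **Scenario summary, main purpose 2**, gives the surgical safety outcomes as "the incidence of surgical transfer and the incidence of postoperative complications". Transfer is read here as conversion.
- **SAP 3.1** plans complication and mortality rates at 28 days and again at 90 days: "To understand the complication rate and mortality rate within 90 days after surgery".
- **SAP 4.2** is headed "Statistical analysis of the population" but describes only the design and the central data review. It defines no as-started, safety or completer set.
- **SAP 4.3** has one sentence on missing data: "Use multiple interpolation methods to deal with missing data". It does not mention patients who exit or convert.
- **SAP 3.8** defines the primary endpoint by margin: "Successful breast-conserving surgery was determined by a negative tumor margin at least 2-3mm from normal tissue"; 4.4 repeats this. **SAP 3.8.1** words it as "Success rate of breast conserving surgery under single port robotic transaxillary approach".

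**The concern.** Conversion is both a main safety outcome and a reason to leave the study. Only patients who start a robotic operation can meet the criterion; controls have no counterpart. It is also related to outcome, because the SAP's own reasons for converting include complications and technical difficulty.

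If exit ends follow-up or removes the patient from analysis, the robot group's later complication rates describe only the operations that went to plan, compared with an unselected control group. Visits at 28 and 90 days that are not made cannot be recovered by later analysis.

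For the primary endpoint the direction depends on a reading the SAP leaves open. Judged on margin, a converted patient with a clear margin is a success, and dropping that patient does not favour the robot. Judged as success under the robotic approach, dropping conversions inflates the rate. For pain and cosmetic score a bias is plausible but not shown.

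**Working it through.** The SAP states no conversion rate, so there is no figure of its own to reproduce. What follows shows how large the effect could be.

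**Inputs from the SAP.** Robot group n = 20 (summary and 4.1). Background complication rates of 3.9% robotic and 7% open (section 1).

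**Assumptions.** Conversion rate c of 5%, 10% or 15%; complication rate x in converted patients; completers' rate of 3.9%.

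**1. Chance that the rule is triggered.** P(at least 1) = 1 − (1−c)^20; P(at least 2) = 1 − (1−c)^20 − 20c(1−c)^19.

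| c | at least 1 | at least 2 |
|---|---|---|
| 5% | 64% | 26% |
| 10% | 88% | 61% |
| 15% | 96% | 82% |

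Each exit removes 1/20 = 5% of the arm.

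**2. Complication rate over all robotic starts** = (1−c) × 3.9% + c × x. With c = 10%:
- x = 10%: 3.51% + 1.0% = 4.5%
- x = 20%: 3.51% + 2.0% = 5.5%
- x = 35%: 3.51% + 3.5% = 7.0%

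With converted patients out, the figure reads 3.9% in every row.

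**3. Rate in converted patients at which the background difference of 7% − 3.9% = 3.1 points is gone:** x = (7% − (1−c) × 3.9%)/c.
- c = 5%: (7 − 3.705)/0.05 = 66%
- c = 10%: (7 − 3.51)/0.10 = 35%
- c = 15%: (7 − 3.315)/0.15 = 25%

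**4. In whole patients (assumed counts).** One complication among 18 completers and two conversions, both with complications: 3/20 = 15.0% with all kept, 1/18 = 5.6% after exit. If neither converted patient has a complication, the order reverses slightly: 1/20 = 5.0% against 5.6%.

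**5. Primary endpoint (assumed counts).** Two conversions, both with clear margins, and one margin failure among the 18 completers; exact 95% intervals:
- completers only: 17/18 = 94.4% (72.7–99.9%)
- all started, by margin: 19/20 = 95.0% (75.1–99.9%)
- all started, success under the robotic approach: 17/20 = 85.0% (62.1–96.8%)

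The same 20 patients give any of these three results, depending on rules the SAP does not state.

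**The case against.** The strongest reply is that exit is not said to mean discarded. No section says converted patients' data are dropped, and several point towards keeping some. Section 3.1 records day-of-surgery data, and 6.2 requires the intraoperative record within 6 hours. Section 5.2 has adverse events recorded through to outcome, and section 7 sends all clinical and safety endpoint events to the monitoring committee. Conversions themselves can still be counted over all robotic starts. This stands as a limit: the likely loss is later follow-up, and it reaches operation time and blood loss only if the day-of-surgery records are dropped too. It does not remove the problem. The criterion sits beside voluntary withdrawal and inability to continue, and nothing keeps converted patients in follow-up or in the robot group's analysis. The imputation sentence could be applied to them, but values imputed from completers would carry the same selection forward.

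It can also be said that the direction is not proven and the numbers are small. Both are fair. Some reasons for converting need not raise the postoperative complication rate. At 10% conversion, the rates of 4.5% to 7.0% are 0.90 to 1.40 expected events in 20 patients, against 0.78 at 3.9%: a shift of 0.12 to 0.62 of a patient. A significance test is unlikely to turn on that, though the reported rate could. The 3.9% and 7% come from references whose titles concern axillary dissection and nipple-sparing mastectomy, and the SAP does not say whether 3.9% excludes conversions. They serve only as an illustration; the SAP sets no target difference.

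Lastly, on the stated margin definition the primary endpoint is not biased in the robot's favour (94.4% against 95.0%), and exclusion criterion 4 might remove a persistent margin failure before it is counted. That is correct. The case therefore rests on the complication outcomes.

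**Conclusion.** The concern holds and needs to be fixed before analysis. As written, the exit rule takes outcome-related patients out of one arm, and no section of the SAP puts them back. The 28- and 90-day robot complication rates would be expected to look too favourable.

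The size cannot be fixed from the document. Over the assumed conversion rates of 5% to 15%, at least one patient is affected with probability 64% to 96%. With 10% converting and x between 10% and 35%, the understatement is 4.5 − 3.9 = 0.6 to 7.0 − 3.9 = 3.1 percentage points.

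This rests on two conditions: that exit ends follow-up or analysis, and that converted patients have more complications than completers. The first is the plain reading, though not an explicit statement; the second is an expectation supported by section 3.5. If the two rates are equal there is no bias. For the primary endpoint the finding is only that the handling of conversions is undefined.

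**What to change.** - **3.3.3:** remove conversion as a reason to leave follow-up and analysis. The surgeon's decision to convert is unaffected.
- **4.2:** define the primary analysis set as all patients in whom the study operation was started, with every robotic start kept in the robot group whether or not converted. Continue the scheduled visits for all of them. Use all robotic starts as the denominator of the conversion rate.
- **3.8, 3.8.1 and 4.4:** state before analysis how a conversion counts for the primary endpoint, reconciling the margin definition with the wording of 3.8.1. The choice is the sponsor's. Report margin status in all started patients whichever is chosen.
- **4.3:** state that converted patients' outcomes are not imputed from completers. Keep the completers-only analysis as a sensitivity analysis.

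The cost is wording. The visits are already in the schedule in 3.6 and intraoperative data are already recorded. The only downside is that the robot figures may look slightly less favourable.
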